A meta-analysis of 12 studies in which 298 patients suffering ICC were treated with Yttrium-90 (Y-90) radioembolization reported overall median survival of 15.5 months⁶. TARE can be offered to patients with adequate performance status according to Eastern Cooperation Oncology Group (ECOG) performance score, blood cell count, liver function, and kidney function⁴. Additionally, TARE is being increasingly used for the treatment of other non-HCC solid tumors in the liver including colorectal cancer metastasis, uveal melanoma metastasis, and neuroendocrine metastasis. Using this approach, radioactive microspheres are delivered via a catheter placed in the hepatic artery branch supplying the tumor, thereby providing a localized and sustained release of radiation. The microspheres used are 20-30 μ m diameter glass beads containing Y-90. Y-90 is a pure beta emitter. It decays to stable Zirconium-90 with a half-life of 64 hours and has an average energy emission of 0.94 MeV. The maximum tissue penetration in the liver is 10 mm^{7,8,9}. Lobar doses range from 110-150 Gy, but radiation delivered to malignant tissue is dependent on distance from the yttrium source. Consequently, treatment response after radioembolization is between 25-60% when based on modified response criteria in solid tumors (mRECIST)^{9,6,10}.

Ultrasound contrast agents

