2.2.1 Secondary

Tumor complete response (CR) and partial response (PR) on mRECIST reads of contrast-enhanced CT or MRI obtained 3-6 months after treatment determined by two independent readers

Changes in Liver Function Tests (LFTs)

Observed and self-reported adverse events

Time required to next treatment

Overall survival

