3.4 Duration of Follow Up

After the subjects have completed treatment, they will be followed through the electronic medical record (EMR) system for up to 1 year to document long term outcomes.

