11.1 Study Hypotheses

H1: Contrast reperfusion time, degree of tumor enhancement relative to the surrounding parenchyma, tumoral IFP and 3D morphological features of the vasculature quantified via CEUS before therapy correlate with SoC mRECIST reads of non-HCC tumor patients treated with TARE.

H2: mRECIST reads for non-HCC tumor patients receiving TARE combined with microbubble inertial cavitation have more complete response (CR) and partial response (PR) reads compared to the historical group treated with TARE alone.

H3: Patient's time to required next treatment and overall survival are longer for non-HCC tumor patients receiving TARE combined with microbubble inertial cavitation compared to the historical group treated with TARE alone.

H4: Observed and self-reported adverse events, and changes in liver function tests (LFTs) one month post-TARE in non-HCC tumor patients receiving TARE combined with microbubble inertial cavitation are similar compared to the historical group treated with TARE alone.

H5: Values of tumor perfusion and residual vascularity quantified by CEUS 2-4 hours, 1 week, and 2 weeks after TARE therapy are lower in CR and PR mRECIST reads of non-HCC tumor patients treated with TARE.

H6: Reductions of tumor perfusion and residual vascularity values quantified by CEUS 2-4 hours, 1 week, and 2 weeks after TARE therapy are more frequent in CR and PR mRECIST reads of non-HCC tumor patients treated with TARE.

H7: Tumoral response in mRECIST reads of MRI or CT (obtained clinically from patients treated with TARE) at 1 month post treatment will agree with response in their mRECIST reads at 3-6 months.

H8: Values of IFP quantified by SHAPE 2-4 hours, 1 week, and 2 weeks after TARE therapy are lower in CR and PR mRECIST reads of patients treated with TARE.

H9: Reductions of IFP values quantified by SHAPE 2-4 hours, 1 week, and 2 weeks after TARE therapy are more frequent in CR and PR mRECIST reads of patients treated with TARE.

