11.2 Analysis Plans

In general, categorical data will be summarized as counts and percentages (or proportions) and continuous data will be summarized with descriptive statistics such as mean, standard deviation (SD), median, and range. All statistical analysis will be performed by [name] using SAS version 9.4 (Cary, NC). All statistical tests will be conducted at a nominal $\alpha=0.05$ level. For H1 (see Section 11.1 above), the respective relationships between the CEUS-derived contrast reperfusion time, degree of tumor enhancement relative to the surrounding parenchyma, tumoral IFP and 3D morphological features of the vasculature with the patients' subsequent mRECIST diagnosis (3 levels: stable disease, partial response, or complete response) will be evaluated by testing for mean difference in the CEUS measures between response levels by analysis of variance (ANOVA). Historical controls ($n=20$) will be identified from a pool of recently treated non-HCC patients at Jefferson that meet study eligibility criteria for the study and match our enrollees by propensity score based on a logistic regression model including patient age, tumor size, bilirubin and ECOG performance score and utilizing a greedy matching algorithm. Testing for the effect of radioembolization on tumor response in H2 will be conducted using non-parametric Mann-Whitney U-tests of the differences in mRECIST distributions between historical controls and enrolled patients. The difference in time-to-event endpoints (i.e., to next treatment or death, respectively) between the treated and historical control patients for H3 will be estimated and tested using Kaplan-Meier survival methods and log-rank tests. Differences in safety data will be evaluated for H4 with descriptive statistics, but not statistical hypothesis tests. A similar ANOVA approach taken for evaluating H1 will be taken for evaluating the means of CEUS measures at different times (2-4 hours, 1 week, and 2 week, respectively) of tumor perfusion and residual vascularity values between response levels to address H5 and SHAPE IFP values for addressing H8, as well as the means of changes from baseline in these measure for addressing H6 and H9. The agreement on response between mRECIST response diagnoses at 1 month and 3-6 months post-TARE will be tested using McNemar's test.

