11.4 Sample Size Considerations

Sample size for this pilot study is primarily driven by patient availability and larger, multi-center randomized trials will likely be needed to fully demonstrate efficacy. However, for the primary objective, a sample size of 20 patients (of which we expect 25% having stable disease, 50% partial responders, and 25% complete responders) will provide 80% power to detect a 0.76 standard deviation difference in CEUS measurement means (e.g., mean contrast perfusion time) between mRECIST response levels, by analysis of variance (ANOVA) with a nominal 5% type I error rate. Similarly, in analyses comparing the prospective treated patients to matched historical control patients, 20 patients per arm will provide 80% power to detect a relative effect size of 0.66 standard deviations by t-test with a nominal 5% type I error rate (i.e., a moderately large, but reasonable effect given our current data in HCC patients).

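### Time to next treatment (H3) has no rule for patients who die first; on the natural reading they are censored, and one minus Kaplan-Meier then overstates the probability of next treatment in each group

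*Combined protocol and SAP*

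**What the plan says.** H3 in Section 11.1 is that "Patient's time to required next treatment and overall survival are longer for non-HCC tumor patients" given TARE with cavitation than for historical controls given TARE alone. The secondary endpoints in Section 2.2 include "Time required to next treatment", with no definition of the event or of censoring, and list overall survival separately. Section 11.2 covers both in one sentence: "The difference in time-to-event endpoints (i.e., to next treatment or death, respectively") "will be estimated and tested using Kaplan-Meier survival methods and log-rank tests" is the stated method, applied to treated patients against historical controls.

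Patients are "followed through the electronic medical record (EMR) system for up to 1 year" (Section 3.4). The only survival figure in the documents is in Section 1.1, where a pooled analysis of intrahepatic cholangiocarcinoma (ICC) treated with Y-90 "reported overall median survival of 15.5 months". No section states what happens to a patient who dies before a next treatment, and none names a competing-risk method.

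**The concern.** The word *respectively* makes next treatment and death two endpoints, not one composite. In a Kaplan-Meier analysis of next treatment, a death without one must be either an event or a censored time. Counting it as an event would create the composite that the wording appears to exclude, so censoring is what an analyst following the text would most naturally do.

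Censoring at death treats the patient as someone who could still be retreated later. The curve then describes a setting in which nobody dies, and its complement is not the proportion of patients who go on to a next treatment. H3 treats a longer time to next treatment as favourable. The controls are historical and matched on four named variables (age, tumour size, bilirubin and ECOG score), which do not include tumour type, so mortality could differ between the groups. If it does, the next-treatment curves alone do not show whether patients spent longer alive without further treatment.

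**Working it through.** **The plan's own figures.** None is given for this endpoint: there is no event count, hazard ratio or power for H3. The nearest is Section 11.4, "20 patients per arm will provide 80% power to detect a relative effect size of 0.66 standard deviations by t-test". It reproduces as a paired t-test with 20 pairs, two-sided 5% (79.9% power), but concerns a difference in means and does not bear on this point.

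**Inputs.**
- Horizon t = 12 months (Section 3.4).
- Median survival 15.5 months (Section 1.1), used as a stand-in for the median time to death before next treatment. This is an assumption.
- Median time to next treatment: not in the documents; assumed 6, 9, 12 or 18 months.
- Constant hazards: a for next treatment and d for death first, each ln 2 divided by its median. Everyone is assumed followed to 12 months.

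**Direction.** With deaths censored, 1 − KM accumulates the next-treatment hazard weighted by the probability of no next treatment. The cumulative incidence weights the same hazard by the probability of being alive with no next treatment. The second weight is never larger, so 1 − KM cannot fall below the cumulative incidence, whatever the hazards.

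**Deaths expected.** 1 − 0.5^(12/15.5) = 41.5% by 12 months.

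**Formulas.**
- 1 − KM = 1 − exp(−a·t)
- Cumulative incidence = a/(a+d) × [1 − exp(−(a+d)·t)]

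**Worked case, 9-month median.** a = ln 2/9 = 0.0770 and d = ln 2/15.5 = 0.0447 per month.
- 1 − KM = 1 − exp(−0.924) = 60.3%
- Cumulative incidence = 0.0770/0.1217 × [1 − exp(−1.461)] = 48.6%
- Gap = 11.7 points

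With the death median held at 15.5 months:

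| Next-treatment median (months) | 1 − KM | Cumulative incidence | Gap (points) | Die first, of 20 |
|---|---|---|---|---|
| 6 | 75.0% | 61.6% | 13.4 | 4.8 |
| 9 | 60.3% | 48.6% | 11.7 | 5.6 |
| 12 | 50.0% | 39.9% | 10.1 | 6.2 |
| 18 | 37.0% | 29.2% | 7.8 | 6.8 |

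Gap in points when the death-first median is varied as well:

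| Death-first median (months) | Next treatment 6 | 9 | 12 | 18 |
|---|---|---|---|---|
| 10 | 19.3 | 16.8 | 14.4 | 11.1 |
| 15.5 | 13.4 | 11.7 | 10.1 | 7.8 |
| 24 | 9.1 | 8.0 | 6.9 | 5.3 |
| 36 | 6.3 | 5.5 | 4.8 | 3.7 |
| 60 | 3.9 | 3.4 | 2.9 | 2.3 |

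**Two groups with unequal mortality.** Give both a 9-month next-treatment median, with death medians of 15.5 and 31 months (d = 0.0447 and 0.0224).
- 1 − KM: 60.3% in both.
- Cumulative incidence of next treatment: 48.6% and 54.0%.
- Next treatment or death, 1 − exp(−(a+d)·12): 1 − exp(−1.461) = 76.8% and 1 − exp(−1.193) = 69.7%.

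The Kaplan-Meier curves for next treatment are identical although the second group does better. The cumulative incidence alone is lower in the group with more deaths. Only the composite ranks the groups by time alive without further treatment.

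**The case against.** Much of the case for leaving the plan alone is sound.

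- **Censoring is not written down.** A reader might infer that the plan prescribes censoring at death. It does not. The documented gap is a missing rule, and censoring is its most natural consequence.
- **The log-rank test is not invalid.** A reader might conclude that the H3 test is wrong. With deaths censored it is still a valid comparison of the cause-specific hazard of next treatment. What fails is reading 1 − KM as the proportion retreated, or the test as a comparison of treatment-free time alive.
- **The group with more deaths is not shown to look better.** A reader might infer that it would. In the constant-hazard example the two curves coincide. A reversal would need the patients who die to be those otherwise headed for retreatment, and the documents give no information on that.
- **The size is soft.** The next-treatment medians are assumed. The 15.5 months is all-cause survival in ICC, including deaths after later treatment, while the trial also enrols other non-HCC tumours and requires medically stable patients with bilirubin no higher than 2 mg/dL. Death before next treatment may be rarer, which is why the range extends down to about 2 points.
- **The stakes are limited.** Overall survival is tested alongside, so excess deaths would not be hidden. Section 11.3.2 describes these outcomes as secondary and likely to run past the study's timeline. With 20 per group, a 50% proportion has a 95% interval of about ±22 points (1.96 × √(0.25/20)), wider than the bias in any scenario above.

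What stands is that the rule is missing, the direction of the bias is certain if deaths are censored, and more patients would not remove it. A separate overall survival test with 20 per group may also be too imprecise to show whether mortality differed.

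**Conclusion.** The point holds as a missing rule with a predictable consequence. If patients who die first are censored, as the wording of Section 11.2 most naturally implies, 1 − KM overstates the probability of next treatment in each group, whatever the hazards. The illustrative 12-month overstatement is about 8 to 13 points at the cited median survival, and about 2 to 19 points over the wider range. Both ranges rest on constant hazards and assumed next-treatment medians, and the first also takes all-cause ICC survival as the death-first hazard.

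The planned log-rank test may stand as a cause-specific comparison. A longer time to next treatment should not be taken as benefit on its own if mortality differs between enrolled patients and controls. The documents do not support going further and saying that the H3 test is invalid or that it would favour the group with more deaths. The matter deserves correction before analysis, but it concerns a secondary endpoint in a 20-patient pilot and leaves the primary analysis untouched.

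**What to change.** In Section 11.2:

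1. State how a death before any next treatment is handled.
2. Estimate the probability of next treatment by cumulative incidence with death as a competing event, in place of 1 − KM.
3. Keep the log-rank test for next treatment, labelled as a comparison of cause-specific hazards.
4. Add next-treatment-free survival (first of next treatment or death) by Kaplan-Meier and log-rank as a supporting analysis for H3. Show both components and the number of deaths before next treatment in each group.
5. Keep overall survival as planned.

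The cost is a few sentences and slightly more analysis. Time to next treatment and survival are already to be recorded (Section 1.3), and the methods are standard in the SAS version named. The drawback is that the composite mixes two kinds of event and reuses deaths already counted under overall survival. For that reason it is proposed as a supporting analysis, not as a replacement for the H3 endpoint.

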11.3.1 Safety Review

Safety outcomes will be compared between the treatment group and the historical group using observed and self-reported adverse events, and changes in LFTs one month post-embolization (performed as part of clinical standard of care). LFTs will include blood tests for alanine aminotransferase, alkaline phosphatase, aspartate aminotransferase, bilirubin, albumin, total protein, and prothrombin time. SPECT imaging will be evaluated for all patients by two blinded radiologists to evaluate if the initial UTMD session skews microsphere distribution in the liver.

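### H4 hypothesizes safety similar to the historical controls, but the plan offers descriptive summaries only, with no interval or limit on interpretation, for 20 versus 20 patients

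*Combined protocol and SAP*

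**What the plan says.** Section 11.1 lists the safety hypothesis as "H4: Observed and self-reported adverse events, and changes in liver function tests (LFTs) one month post-TARE" in patients receiving TARE with cavitation, and states that these "are similar compared to the historical group treated with TARE alone".

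Section 11.2 gives its analysis: "Differences in safety data will be evaluated for H4 with descriptive statistics, but not statistical hypothesis tests". The same section says what descriptive means here. Categorical data get counts and percentages, and "continuous data will be summarized with descriptive statistics such as mean, standard deviation (SD), median, and range". Confidence intervals are not mentioned.

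Section 11.3.1 says "Safety outcomes will be compared between the treatment group and the historical group using observed and self-reported adverse events" together with one-month LFT changes, and names seven LFT measures. It adds no margin, interval or rule for deciding that the groups are similar.

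Section 11.4 gives a power figure for comparisons with the historical controls, but no power or precision for safety. Its caveat about larger randomized trials refers to efficacy. The secondary objective in section 2.1.2 is softer than H4: it is to characterize safety.

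**The concern.** H4 claims more than its analysis can deliver. Similarity is a statement about how large a difference could still be present. Counts, percentages, means and SDs set side by side do not show that. In small groups they will often look alike even when the true rates differ materially.

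The safety of adding cavitation is a secondary objective, and section 1.4.2 says the study aims to define both efficacy and safety. Section 1.4.1 names a specific hepatic risk, sensitization of non-tumor liver to the Y-90 emissions, and lists reasons to expect it to be limited. Section 5.3 says AE rates at these doses have not been fully evaluated alongside radioembolization. One-month LFTs are a planned measure bearing on that risk, so a reader needs to know how precisely the LFT comparison was made.

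**Working it through.** **Inputs.** 20 treated patients and 20 matched historical controls (11.2, 11.4); a 5% type I error rate, sidedness not stated (11.4). The documents define no margin for similarity and give no AE rate for TARE, so the observed counts below are illustrations.

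**The plan's own figure.** Section 11.4 states that "20 patients per arm will provide 80% power to detect a relative effect size of 0.66 standard deviations by t-test".
- A paired two-sided t-test on 20 matched pairs has 79.9% power at 0.66 SD (detectable effect 0.660 SD), so the figure reproduces in that form.
- A two-sample two-sided t-test has 53.0% power (detectable effect 0.91 SD).

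Neither describes H4, for which no test is planned.

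**Difference in AE proportions.** The Wilson limits for one proportion p with n = 20 and z = 1.96 are

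[p + z²/(2n) ± z√(p(1−p)/n + z²/(4n²))] / (1 + z²/n).

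If both groups show the same p with Wilson limits l and u, the unpaired Newcombe 95% interval for the difference is ±√[(p−l)² + (u−p)²].

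| Observed in each group | l | u | 95% interval for the difference |
|---|---|---|---|
| 0/20 | 0 | 0.161 | ±16 points |
| 2/20 | 0.028 | 0.301 | √(0.072² + 0.201²) = ±21 points |
| 4/20 | 0.081 | 0.416 | √(0.119² + 0.216²) = ±25 points |

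At 10/20 in each group the interval is ±28 points.

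**Difference in mean LFT change.** The unpaired half-width in SD units is t(0.975; 38 df) × √(2/20) = 2.024 × 0.316 = 0.64 SD. Analysed as 20 pairs it is 2.093/√20 = 0.47 SD of the within-pair difference. If paired patients are uncorrelated, that equals 0.47 × √2 = 0.66 SD of the individual change.

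**Events in the treated group alone (Clopper-Pearson).**
- 0/20: upper limit 1 − 0.05^(1/20) = 13.9% one-sided, or 1 − 0.025^(1/20) = 16.8% two-sided.
- 1/20: about 25% two-sided.
- 2/20: about 32% two-sided.
- Chance of seeing no event at all: 0.90^20 = 12% for a true 10% rate, and 0.95^20 = 36% for a true 5% rate.

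**What a real similarity claim would need.** Assume a 16.8% rate in both groups. This is the any-AE rate for Optison alone in section 1.1 (47/279); that it equals the 0/20 limit above is a coincidence. With one-sided 2.5% error and 80% power, n per group = 2 × 0.168 × 0.832 × (1.96 + 0.84)² / margin². That gives 220, 98 and 55 per group for assumed margins of 10, 15 and 20 points.

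**The case against.** The strongest reply is that this is a pilot sized by patient availability, that descriptive safety reporting is normal in a pilot, and that declining to test is itself a refusal to make a confirmatory claim. Most of this stands. A test would not help: a doubling of the AE rate from 16.8% to 33.6% would be found with only about 15% power by Fisher's exact test. The objective to characterize safety also fits a descriptive analysis. What does not fit is H4, which asserts similarity and goes beyond that objective.

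A reader might infer that nothing in the plan could contradict similarity. That is too strong. A marked imbalance in AEs or in the seven LFT measures would show in the summaries. Safety is also watched in other ways: blinded SPECT review (11.3.1), CTCAE grading with causality and expectedness (8.3), DSMC reporting (8.4.2) and halting rules (8.5). None of these supplies an interval for H4.

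A reader might also infer that the result will be declared safe, or used to justify larger trials. No section sets a rule for declaring H4 met. Section 11.4 mentions larger trials only for demonstrating efficacy. Section 1.4.1 does call an earlier HCC trial safe, citing results in 28 patients without significant differences, but that describes another study and is not a rule for this one.

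Two limits on the remedy also stand. The Newcombe intervals ignore the matching, although controls are chosen to "match our enrollees by propensity score based on a logistic regression model including patient age, tumor size, bilirubin and ECOG performance score". And an interval covers sampling error only. Section 8.2 has AEs asked about at each study visit, while the controls are already treated patients for whom no equivalent inquiry is described.

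**Conclusion.** The point holds as a mismatch between hypothesis and analysis, of minor severity. H4 asserts similarity, and the planned summaries carry neither an interval nor a limit on interpretation. With 20 per group, identical observed AE rates leave true differences of roughly 16 to 28 points open, and an LFT difference is known only to about ±0.64 SD unpaired. The absence of a visible difference is therefore not evidence of similarity.

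The AE figures assume complete data, unpaired analysis and the illustrative counts shown. Withdrawals are not replaced (11.4.1) and would widen the intervals.

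The absence of hypothesis tests is not itself an error. Nor do 20 patients exclude event rates above 14-17% in general, as a reader might infer from the zero-event calculation. That limit holds only for an event seen in 0 of 20 treated patients.

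**What to change.** - **11.1:** Reword H4 as estimation of the between-group differences in AEs and one-month LFT changes, in line with the objective in 2.1.2.
- **11.2:** Report 95% intervals for the difference in the proportion of patients with any Grade 3 or higher AE and with any hepatic AE. Report the baseline-adjusted difference in each one-month LFT with its interval. Give exact upper limits for treated-group event rates. Say whether the intervals use the matching.
- **11.2 and 11.4:** State that similarity will not be concluded from these data. State that the 13.9% (one-sided) or 16.8% (two-sided) upper limit applies only to an event seen in 0 of 20 treated patients, rising to about 25% at 1/20 and 32% at 2/20 (two-sided).
- **11.2:** Add that the AE intervals reflect sampling error only, because treated patients are asked about AEs at each visit and no equivalent inquiry is described for the controls.

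The cost is a few sentences and some added output. The treated group needs no new patients, visits or data. Control AEs can be graded only as far as existing records allow. The stated safety conclusion becomes less favourable.

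### H5 and H8 compare post-TARE values across response levels without the pre-treatment value, so a positive result alone may be the H1 baseline difference seen again; an exploratory baseline-adjusted analysis should be added

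*Combined protocol and SAP*

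**What the plan says.** Section 11.1 (H1) states that contrast reperfusion time, relative enhancement, tumoral IFP and vascular morphology "quantified via CEUS before therapy correlate with SoC mRECIST reads". Section 11.2 tests this by one-way ANOVA across three response levels (stable disease, partial response, complete response).

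H5 reads: "Values of tumor perfusion and residual vascularity quantified by CEUS 2-4 hours, 1 week, and 2 weeks after TARE therapy are lower" in responders. H8 says the same of IFP measured by SHAPE. Section 11.2 applies a similar ANOVA to the values at 2-4 hours, 1 week and 2 weeks. For H6 and H9 it specifies the same approach for change, "as well as the means of changes from baseline in these measure for addressing H6 and H9".

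No part of Section 11 names a baseline covariate or a model holding the pre- and post-treatment values together. Section 11.5 only refers back to 11.2. Section 5.8 shows that the baseline data will exist: more than five flash-replenishment cycles and triplicate SHAPE readings before TARE.

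The secondary objective (2.1.2) is prediction of response from the 7-14 day exam. Other parts say more. The Study Summary, 1.1 (Study goal) and 2.1 speak of assessing response sooner than current practice, and 2.1.3 of an early biomarker of radiotherapy response.

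**The concern.** The same patients, in the same three response groups, are measured before and after TARE. If the groups already differ before treatment, as H1 proposes, and a patient's two values are correlated, the groups will also differ afterwards, even when the second exam carries no new information. H5 and H8 cannot separate these explanations.

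The overlap is exact for IFP, which appears in H1 and H8. For H5 it is looser, because perfusion and residual vascularity are not named identically in H1. However, 2.1.1 lists volumetric perfusion among the pre-treatment measures, and H6 needs baseline values of the H5 measures to form a change.

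H6 and H9 have a different, smaller weakness. Subtraction removes a constant offset. It does not remove dependence of change on the starting level, through regression to the mean or through falls proportional to baseline.

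At stake is interpretation: whether the trial can say that an early post-treatment exam shows something the pre-treatment exam did not.

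**Working it through.** **Inputs.** From 11.4: 20 patients, expected 25/50/25%, so groups of 5/10/5; alpha 0.05; 80% power; effect 0.76. The documents give neither the baseline-post correlation (rho) nor the true baseline difference. Assumed: rho 0.3 to 0.9; baseline difference f = 0.76, or a smaller one of 0.76 SD between adjacent levels.

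**1. The plan's own figure.** Section 11.4 says the sample "will provide 80% power to detect a 0.76 standard deviation difference in CEUS measurement means". With 0.76 as Cohen's f, the noncentrality is 20 × 0.76² = 11.55 and, with 2 and 17 df, power is 0.7999, so the figure reproduces. Taken as 0.76 SD between adjacent levels, power is 0.49, so f is the reading used. For equally spaced means, f = d × √0.5, so d = 0.76/√0.5 = 1.075 SD between adjacent levels.

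**2. Post-TARE exam adds nothing.** Let B be baseline (within-group SD 1) and Y = rho × B + √(1 − rho²) × noise, so Y depends on response only through B.

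- Post value: noncentrality = 20f² × rho² = 11.55 × rho².
- Change Y − B: group differences are (rho − 1) times those at baseline and within-group variance is 2 − 2rho, so noncentrality = 20f² × (1 − rho)²/(2 − 2rho) = 5.776 × (1 − rho).

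| rho | Noncentrality, post | H5/H8 reject | Noncentrality, change | H6/H9 reject | ANCOVA rejects |
|---|---|---|---|---|---|
| 0.3 | 1.04 | 12.2% | 4.04 | 35.9% | 5% |
| 0.5 | 2.89 | 26.6% | 2.89 | 26.6% | 5% |
| 0.7 | 5.66 | 48.1% | 1.73 | 17.4% | 5% |
| 0.9 | 9.36 | 70.7% | 0.58 | 8.8% | 5% |

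The ANOVA columns are from the noncentral F; 20,000 simulated trials per setting agree to within about half a percentage point. The ANCOVA column is simulated. With the smaller baseline difference, H5/H8 reject in 9, 15, 26 and 41%, H6/H9 in 20, 15, 11 and 7%, and ANCOVA stays at about 5%. With no baseline difference, all three hold 5%.

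**3. Proportional fall.** Let Y = 0.5B + noise of SD 0.5. Change = −0.5B + noise, with group effect 0.5 × 0.76 = 0.38 and within-group SD √(0.25 + 0.25) = 0.707, so f = 0.38/0.707 = 0.537. The change ANOVA rejects in 48-49%.

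**4. Fixed group offset at both exams, correlated noise.** With the offset at f = 0.76 and rho 0.5, 0.7, 0.9, the post-value ANOVA rejects in about 80%, the change ANOVA in 5%, and ANCOVA in 22, 13 and 7%. With the smaller offset, ANCOVA rejects in 15, 10 and 6%.

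**5. Direction.** The factor (rho − 1) is negative, so the step 2 artefact in change runs against the one in the post value. If responders start lower, H5 is favoured and H6 opposed; if they start higher, the reverse. Simulated, H5 and H6 are both significant in the hypothesised direction in at most 0.6% of trials (step 2), 0.1% (step 3) and 2.7% (step 4).

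**6. Cost of the covariate.** Going from 17 to 16 residual df takes power at f = 0.76 from 80.0% to 79.5%, if baseline is balanced across groups and unrelated to the post value. If the groups differ at baseline by f = 0.76, the covariate overlaps with response. The expected baseline sum of squares is 10 × 1.075² + 19 = 11.56 + 19 = 30.56, and response accounts for 11.56/30.56 = 38% of it. Noncentrality falls to roughly 11.55 × 0.62 = 7.2; simulated power in that setting is about 56%.

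**The case against.** The strongest reply is that 2.1.2 asks only whether the 7-14 day exam predicts response. An unadjusted association answers that. In step 2 the post-TARE values really do differ by response, so those rejections are not false positives for H5 as worded. This stands, and it is why the planned ANOVAs should remain.

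Second, the plan pairs each post-value test with a change test (H5 with H6, H8 with H9). By step 5, the artefact rarely makes both significant in the hypothesised direction. This also stands, but 11.2 does not say that the two must agree before anything is concluded, so either could be reported alone.

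Third, ANCOVA is not neutral: step 4 shows it rejecting in 6-22% where a fixed offset persists, while the change score holds 5%. This argues against replacing the planned tests, not against adding one.

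Fourth, this is a 20-patient pilot, 1.4.2 says no treatment decisions rest on CEUS data, and the correlation is assumed. That limits the weight of the point but does not remove it.

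A reader might infer that all four hypotheses ignore baseline, or that a positive result can never be told apart from H1. The documents do not support this: 11.2 specifies change from baseline for H6 and H9, and the paired tests carry information that H5 or H8 alone does not.

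**Conclusion.** The point holds for H5 and H8 taken alone. If the baseline difference is f = 0.76 and rho is 0.3-0.9, they are significant in about 12-71% of trials in which the post-TARE exam adds nothing to baseline (9-41% with the smaller difference). For H6 and H9 it holds in a weaker form: raw change rejects in 9-36% through regression to the mean, or 48-49% with a 50% proportional fall. The direction depends on which group starts higher, and a constant offset gives no excess.

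These rates rest on assumed correlations and baseline differences; if H1 is false, the problem disappears. A reader might also infer that the early-monitoring aim is untestable as planned. That goes too far: the prediction objective is answered as written. What the plan lacks is an analysis that shows whether the early exam carries information beyond the pre-treatment one, which its wider claims about earlier assessment and an early biomarker call for.

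**What to change.** In 11.2, keep the planned ANOVAs for H5, H6, H8 and H9 as the answer to the prediction objective. For each time point, add an ANCOVA of the post-TARE value by response level with the same patient's pre-treatment value as covariate (or a partial rank correlation), labelled exploratory. State that the early exam will be said to add to the pre-treatment exam only if this analysis supports it and the change-score result agrees, since neither is protected under every pattern (steps 2 to 4). A non-significant ANCOVA should not be read as showing that nothing is added.

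The cost is SAP text and a little more analysis; no new data are needed. In degrees of freedom the price is one (80.0% to 79.5% power at f = 0.76). The adjusted test loses more if the groups differ strongly at baseline (about 56% in step 6), which is a further reason to call it exploratory.
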